Historically DGF has been defined as the requirement for dialysis during the first week after renal transplantation, however the postoperative requirement of hemodialysis or peritoneal dialysis is not standardized and the decision to

dialyze varies from center to center and among consultants (Daly et al, 2005). More recently, efforts have been made to scientifically quantify DGF in a more stringent manner with various alternative definitions of DGF including; (1) the number of days to achieve a creatinine clearance of >10 mL/min, calculated by the Gault-Cockroft formula (Giral-Classe et al, 1998), (2) a serum creatinine level of >3 mg/dL on the fifth day post-transplant (Humar et al, 2000), (3) the need for dialysis within 72 hours after transplantation (Hetzel et al, 2002), (4) serum creatinine level changes, including an increase, remaining unchanged, or decreasing by less than 10% per day immediately after surgery during three consecutive days for >1 week (Boom et al, 2000), (5) a rising serum creatinine level above that before surgery, or urine output of <300 mL within 6 hours of transplantation, despite diuretics and adequate volume (Gonwa et al, 2002), (6) urine output of <1 L in the first 24 hours or a decrease in serum creatinine of <20-30% reflected in a poor glomerular filtration rate (GFR) (Halloran and Hunsicker, 2001), and (7) calculating the creatinine reduction ratio on day two following surgery (Salahudeen et al, 2004). However despite these alternative suggestions, the conventional definition of "requirement for dialysis in the first week post-transplant" remains the most utilized and published definition for DGF, with "need for dialysis" being easily measured and clinically relevant.

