4.6 Study Variables

4.6.1 Efficacy Variables

4.6.1.1 Primary Efficacy Endpoints

For patients who do not require dialysis in the first 7 days:

- Proportion of patients enrolled with serum creatinine >3mg/dL on postoperative day 5.
- Proportion of patients with serum creatinine reduction ratio of < 30% from 24 to 48 hours post-transplant.

For patients who require dialysis in the first 7 days: (Excluding patients who get dialysis for hyperkalemia)

- The proportion of patients enrolled who require at least one session of dialysis in the first 7 days post transplant.
- Number of dialysis sessions per patient in the first 7 days post transplant.

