5.5 Confidentiality

All records identifying the subject will be kept confidential and, to the extent permitted by the applicable laws and/or regulations, will not be made publicly available.

Subject names will not be supplied to the sponsor. Only the subject number and subject initials will be recorded in the case report form, and if the subject name appears on any other document (e.g., pathologist report), it must be obliterated before a copy of the document is supplied to the sponsor. Study findings stored on a computer will be stored in accordance with local data protection laws. The subjects will be informed in writing that representatives of the sponsor, EC/IRB, or Regulatory Authorities may inspect their medical records to verify the information collected, and that all personal information made available for inspection will be handled in strictest confidence and in accordance with local data protection laws.

If the results of the study are published, the subject's identity will remain confidential.

The investigator will maintain a list to enable subjects' records to be identified.

- 6 Statistical Methods And Determination Of Sample Size
- 6.1 Statistical And Analytical Plans
- 6.2 Determination of Sample Size

The sample size calculations were based on a conservative assessment aimed to show $\sim 50\%$ reduction in DGF rates with C1INH application. Data from the Cedars-Sinai Medical Center Renal Transplant Program for DGF rates are shown below:

CONFIDENTIAL

	Transplants 7/1/2011 until 7/1/2013
	N=237
	DGF Rate
ECD	27/36 (75%)
DCD	9/13 (69%)
Final Cr >/=1.5	28/37 (76%)
Non-ECD/DCD/Cr<1.5	33/100 (33%)

Briefly, the DGF rates at our center for the proposed study groups are >70% compared to 33% for SCD donors. Thus, a conservative proposal is explored below. The sample size calculations showing 35 subjects per group would sufficiently power the study (80%) to show 50% reduction when an anticipated DGF rate of 50% for the study group is anticipated.

The "proportion" below is the proportion with DGF. A 2-sided test (to be more conservative) was performed. We assumed a 50% DGF rate in the Placebo group. Treated group DGF rate vary: 20%, 25%, and 30%. sample size per group for 80% and 90% power are shown.

Two group continuity corrected χ^2 test of equal proportions (odds ratio = 1) (equal n's)

-	1	2	3	4	5	6
Test significance level, \Box	0.050	0.050	0.050	0.050	0.050	0.050
1 or 2 sided test?	2	2	2	2	2	2

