Treated Group	0.200	0.250	0.300	0.200	0.250	0.300
proportion, π_1 Placebo Group	0.500	0.500	0.500	0.500	0.500	0.500
proportion, π_2 Odds ratio,						
$\psi = \pi_2 (1 - \pi_1) / [\pi_1 (1 -$	4.000	3.000	2.333	4.000	3.000	2.333
π_2)]						
Power (%)	80	80	80	90	90	90
n per group	45	66	103	58	85	134

A two group continuity corrected χ^2 test with a 0.05 two-sided significance level will have 80% power to detect the difference between a Treated Group proportion, π_1 , of 0.20 and a Placebo Group proportion, π_2 , of 0.50 (odds ratio of 4.00) when the sample size in each group is 45.

Two group continuity corrected χ^2 test of equal proportions (odds

Note: The odds ratio (OR) is the OR for DGF. In Column 1, OR = 4, so the odds of DGF in the Placebo group is 4 times the odds of DGF in the Treated group.

One-sided tests:

proportion, π_1

 π_2)

ratio = 1) (equal n's)						
	1	2	3	4	5	6
Test significance level, \Box	0.050	0.050	0.050	0.050	0.050	0.050
1 or 2 sided test?	1	1	1	1	1	1
Treated Group	0.200	0.250	0.300	0.200	0.250	0.300

Placebo Group	0.500	0.500	0.500	0.500	0.500	0.500
proportion, π_2 Odds ratio,						
$\psi = \pi_2 (1 - \pi_1) / [\pi_1 (1 -$	4.000	3.000	2.333	4.000	3.000	2.333

 Power (%)
 80
 80
 80
 90
 90
 90

 n per group
 37
 54
 83
 48
 71
 111

Statistical Assumptions

- Since this study is a Phase I/II, we will primarily explore the safety of the proposed dose in the renal transplant population receiving high-risk ECD and DCD kidneys. Our previous experience in a population of highly-HLA sensitized renal allograft recipients showed that administration of 20U/kg (8 doses in 1 month) was safe and without AE or SAE when compared to placebo (NCT01134510). Based on the calculations above, we propose a randomized, placebo controlled trial of C1INH vs. placebo entering 35 eligible patients into both arms of the study.
- 7 Adverse Events (AEs)
- 7.1 Adverse Event (AE) Monitoring
- 7.2 Adverse Event (AE) Definitions
- 7.2.1 Adverse Events (AEs)

An AE is any untoward medical occurrence in a subject or clinical investigation subject administered with a pharmaceutical product. The AE does not necessarily have to have a causal relationship with this treatment. An AE can therefore

be any unfavorable and unintended sign (including an abnormal laboratory finding), symptom, or disease temporally associated with the use of an investigational product, whether or not considered related to the medicinal product.

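### Four primary efficacy endpoints carry no significance level, ranking, success rule or multiplicity control, while the sample size covers one DGF proportion that is tied to none of them

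*Combined protocol and SAP*

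**What the plan says.** Section 4.6.1.1, repeated in the synopsis (2.2), lists the primary efficacy endpoints in two blocks.

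- For patients who need no dialysis in the first week: "Proportion of patients enrolled with serum creatinine >3mg/dL on postoperative day 5" and "Proportion of patients with serum creatinine reduction ratio of < 30% from 24 to 48 hours post-transplant".
- For patients who do need it, leaving out those dialysed for hyperkalemia: "The proportion of patients enrolled who require at least one session of dialysis in the first 7 days post transplant" and "Number of dialysis sessions per patient in the first 7 days post transplant".

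Neither place ranks the four, assigns them a significance level, or says how many must succeed. Section 6.1 has no text before 6.2 begins, and the statistical row of the synopsis promises summaries and comparisons without naming any.

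Section 6.2 calculates the sample size for one quantity. Its tabulated proportion "below is the proportion with DGF. A 2-sided test (to be more conservative) was performed". The worked statement concerns a continuity-corrected chi-square "test with a 0.05 two-sided significance level will have 80% power", and a second table headed "One-sided tests" follows, also at 0.05. Section 6.2 does not define DGF. The Introduction says that dialysis in the first week "remains the most utilized and published definition for DGF". The only listed efficacy endpoint that uses the term DGF is the four-grade scale in section 4.6.1.2, which is secondary.

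**The concern.** The sample size answers one question and the primary endpoint list asks four, with nothing to connect them. A report that followed the plan to the letter could present whichever endpoint came out significant as the primary result.

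This matters beyond labelling. Sections 4.5.1 and 4.5.7 claim power for a difference in DGF, and section 2.1 intends to use the results to choose a Phase III dose and endpoint. Picking the best of four small-sample comparisons would carry selection error into those choices.

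The block headings add a second difficulty. Read literally, the proportion dialysed is taken among patients who require dialysis, which makes it 100% in both arms. All four endpoints are also placed under groups defined by something that happens after randomisation.

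**Working it through.** **1. The plan's own figure.** Inputs from section 6.2: placebo 0.50, treated 0.20, two-sided 0.05, 80% power, continuity-corrected chi-square.

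- Uncorrected: n' = [1.960·√(2·0.35·0.65) + 0.842·√(0.20·0.80 + 0.50·0.50)]² / 0.30² = (1.322 + 0.539)² / 0.09 = 38.5.
- Corrected: n = (n'/4)·[1 + √(1 + 4/(n'·0.30))]² = 9.62 · 2.160² = 44.9, so 45 per group, as tabulated.

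The other eleven entries also reproduce. Each is a sample size for a single test of one proportion.

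**2. Upper figure for four tests.** Assume each endpoint is tested at 5%, any one counts, and the tests are independent and of exact size:

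1 − 0.95⁴ = 0.185.

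For jointly normal test statistics this is the ceiling whatever the correlations. The floor is 5%, at perfect correlation.

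**3. Effect of correlation.** The documents give none, so these values are assumed.

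| Common correlation | 0 | 0.3 | 0.5 | 0.7 | 0.8 | 0.9 |
|---|---|---|---|---|---|---|
| At least one false positive | 18.5% | 17.4% | 15.6% | 13.1% | 11.4% | 9.4% |

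A common correlation does not fit the layout well, because the two blocks are disjoint sets of patients. With correlation only within each block, the result is 17.9% (creatinine pair 0.5, dialysis pair 0), 16.2% (0.5 and 0.8) or 13.8% (0.8 and 0.95).

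**4. The test the plan names.** The continuity-corrected chi-square is conservative at this size. Its exact type I error at a nominal 5%, for true proportions of 0.3 to 0.7, is 2.4 to 2.8% with 35 per arm and 1.9 to 2.4% with 17 per arm, roughly the non-dialysed number if half are dialysed. Allowing the session count a full 5% and assuming independence:

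- larger sizes: 1 − 0.976² · 0.972 · 0.95 = 12.0%
- smaller sizes: 1 − 0.981² · 0.976 · 0.95 = 10.8%

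**5. Patient-level simulation under no effect, 35 per arm.** Assumptions not taken from the documents: dialysis rate 50% or 70%; 50% marginal rates for both creatinine endpoints; latent correlation 0.3 or 0.7; sessions distributed as 1 + Poisson(1.2), compared by Mann–Whitney in all patients or in dialysed patients only. The dialysis proportion was taken over all patients. There were eight scenarios of 2,500 runs, with a simulation error near √(0.10·0.90/2500) = 0.6 percentage points.

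| Chi-square for the three proportions | At least one p < 0.05 |
|---|---|
| Uncorrected | 11.0 to 18.6% |
| Continuity-corrected | 7.0 to 10.7% |

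**6. Cost of splitting alpha instead.** Bonferroni at 0.05/4 = 0.0125 gives 1 − 0.9875⁴ = 4.9% under independence. The DGF comparison would then need 62 per group (0.50 against 0.20) or 91 (0.50 against 0.25), continuity-corrected, at 80% power. With the planned 35 its power would be 56% or 36% by the uncorrected formula.

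**The case against.** The strongest reply is that familywise control is a confirmatory standard and this is not a confirmatory trial. The primary objective in section 2.1 is safety, section 6.2 repeats that emphasis, and choosing an endpoint for Phase III is a stated secondary objective, so carrying several candidates is deliberate. That stands as a reason for modest severity. It does not explain why all four are called primary, or why a powered DGF comparison is claimed and then not identified.

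The error rates are also open to challenge, and much of that challenge stands. A reader might infer that the plan tests each endpoint at an unadjusted 5% and so carries an error rate of 11 to 19%. The documents do not support this. The 0.05 appears only in section 6.2, for one DGF comparison and with both sidedness options. No rule says that one success out of four is enough, and if all four were required there would be no inflation. Read literally, the dialysis proportion cannot differ between arms, which leaves three tests and a ceiling of 1 − 0.95³ = 14.3%. The conservative test lowers the figure further.

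A reader might also infer that section 6.2 relies on a 5% level it does not have. It does not: the other endpoints leave the level of the single DGF test unchanged.

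Finally, the Introduction notes that the decision to dialyse is not standardised and varies between centres and consultants, which is a documented reason for having creatinine endpoints. This is an argument for keeping them, though not for leaving four primaries unranked.

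**Conclusion.** The concern holds as a gap in specification. There are four primary efficacy endpoints with no level, order, success rule or multiplicity control, and a sample size for a DGF proportion that is not linked to any of them.

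The size is conditional. If each endpoint were tested at 5% and any one counted, the familywise error could reach 18.5% with independent, exact-size tests. It is about 7 to 11% in the simulated scenarios with the continuity-corrected chi-square. Both figures rest on an any-one-of-four rule that the plan neither states nor excludes, and on assumed correlations and event rates. They show what the silence permits; they are not the plan's own error rate.

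Severity is modest because the trial is Phase I/II and puts safety first. The point is still worth correcting, because the plan claims power for DGF and intends to use efficacy results in Phase III decisions.

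**What to change.** Designate one primary efficacy endpoint: the proportion of all randomised patients with at least one dialysis session in the first 7 days after transplant. This is the conventional DGF definition in the Introduction, and over all randomised patients it no longer depends on the post-randomisation block heading. Then:

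- state in section 6.2 that the powered DGF proportion is this endpoint;
- put its test, level and sidedness into section 6.1, since section 6.2 shows both two-sided and one-sided tables;
- reconcile how dialysis given for hyperkalemia is counted, because section 4.6.1.1 now leaves those patients out and a denominator of all randomised patients must say where they go;
- move the other three endpoints to secondary, reported with confidence intervals, and make the same change in the synopsis.

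The cost is small but is more than rewording: the denominator and the treatment of hyperkalemia become part of the endpoint definition. Three endpoints lose primary status. Because the decision to dialyse varies between centres, the creatinine endpoints should stay as supportive secondary results, where they still inform the Phase III endpoint choice. No alpha is spent, unlike a Bonferroni split. The change does not settle whether 35 per group is enough, which is a separate question: the plan's own two-sided table gives 66 per group for 0.50 against 0.25 at 80% power.

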4.6.1.2 Secondary Efficacy Endpoints

- Daily serum creatinine for seven days post transplant or until discharge.
- Daily Calculated Creatinine Clearance for seven days post transplant or until discharge.
- Serum creatinine at 14, 28, 60, and 90 days post transplant.
- Total urine output in hours 16-24, 40-48 post transplant.
- Rate of dialysis use at 14, 28, 60, and 90 days post transplant.
- Dialysis duration at 14, 28, 60, and 90 days post transplant.
- Calculated creatinine clearance at 14, 28, 60, and 90 days post transplant.

CONFIDENTIAL

- Rate of acute cellular and antibody mediated rejection episodes by day 90.
- Patient and graft survival by day 90.
 - Protocol renal transplant biopsy at time of implantation.
 - Incidence of DGF as categorized by a DGF scale of increasing severity as follows:

Grade 1 - immediate urine production and no need for dialysis with creatinine reduction ratio (CRR) between time 0 of transplantation and day 7 post-transplantation >70%

Grade 2 - creatinine reduction ratio (CRR) between time 0 of transplantation and day 7 post-transplantation of >70% with need for dialysis

Grade 3 - creatinine reduction ratio (CRR) between time 0 of transplantation and day 7 post-transplantation <70% with no need for dialysis

Grade 4 - creatinine reduction ratio (CRR) between time 0 of transplantation and day 7 post-transplantation of <70% with need for dialysis

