4.6.4.12 Rate and Duration of Dialysis

Duration of dialysis will be measured by the number of sessions of dialysis treatment needed in the first 7 days post transplant. As for rate of dialysis, one dialysis session will represent the need for dialysis treatment.

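### The four-grade DGF scale has no grade for a never-dialysed patient with slow urine onset and good day 7 creatinine recovery, and the plan does not say which grades count as DGF

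*Combined protocol and SAP*

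**What the plan says.** Section 4.6.1.2 lists as a secondary endpoint "Incidence of DGF as categorized by a DGF scale of increasing severity as follows". The synopsis (Section 2.2) carries the same scale. The grades are:

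- Grade 1: "immediate urine production and no need for dialysis with creatinine reduction ratio" above 70% between time 0 and day 7.
- Grade 2: "day 7 post-transplantation of >70% with need for dialysis".
- Grade 3: "day 7 post-transplantation <70% with no need for dialysis".
- Grade 4: "day 7 post-transplantation of <70% with need for dialysis".

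Urine production appears in Grade 1 only, and what counts as immediate is not defined. Section 4.6.4.12 sets a low threshold for dialysis: "one dialysis session will represent the need for dialysis treatment". The Introduction says that dialysis in the first week "remains the most utilized and published definition for DGF".

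Neither place says which grades count as DGF, how a patient who fits no grade is handled, or how the grades are compared between arms. Section 6.1 has a heading but no text, and the synopsis promises only descriptive and comparative statistics.

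**The concern.** A graded endpoint should give each randomised patient exactly one grade. Grade 1 joins three conditions, and a patient who fails only the urine condition is not picked up by another grade. That patient started slowly but recovered without dialysis, which is a plausible course in this population. All three components are observed after randomisation, so the number of ungraded patients can differ by arm, and any informal way of handling them would be a choice made after the fact.

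Two related matters affect interpretation. First, the endpoint is named an incidence, yet Grade 1 describes good function and no grade is marked as the start of DGF. Second, the declared order puts a never-dialysed patient with CRR below 70% above a dialysed patient with CRR above 70%. Depending on the analysis, avoiding dialysis could then count against treatment.

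The endpoint is secondary, so one supportive analysis is at stake. Section 2.1, however, makes the choice of a Phase III endpoint a study objective, and a scale with a gap cannot be judged fairly as a candidate.

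**Working it through.** The plan gives no rate, power or sample size for this scale, so it has no figure of its own to reproduce. The check applies the definitions as written and then uses assumed counts to show direction.

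**1. Enumeration.** Inputs: the four grade definitions in Section 4.6.1.2. Leaving exact ties aside, there are 2 (urine immediate or not) × 2 (dialysis or not) × 2 (CRR above or below 70%) = 8 combinations.

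| Immediate urine | Dialysis | CRR >70% | CRR <70% |
|---|---|---|---|
| Yes | No | Grade 1 | Grade 3 |
| Yes | Yes | Grade 2 | Grade 4 |
| No | No | **none** | Grade 3 |
| No | Yes | Grade 2 | Grade 4 |

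Seven of 8 are graded and 1 is not. Grade 2 ignores urine, so a slow starter with CRR above 70% is graded if dialysed and loses the grade if spared dialysis. Adding CRR of exactly 70% gives 12 combinations, of which 7 are graded; the 4 extra empty ones are ties.

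**2. Effect of the gap.** Assumed counts for an arm of 35 (the arm size in Section 4.5.7): 25 patients in Grades 2 to 4, and 10 never dialysed with CRR above 70%, of whom u did not produce urine immediately. The share with Grade 2 or higher is:

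- 25/(35 − u) if the ungraded are dropped;
- 25/35 if they are placed in Grade 1;
- (25 + u)/35 if they are counted as DGF.

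| u | Dropped | As Grade 1 | As DGF |
|---|---|---|---|
| 1 | 25/34 = 73.5% | 71.4% | 26/35 = 74.3% |
| 2 | 25/33 = 75.8% | 71.4% | 27/35 = 77.1% |
| 4 | 25/31 = 80.6% | 71.4% | 29/35 = 82.9% |

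Two arms identical in dialysis and CRR, with u = 4 in one and u = 0 in the other, would differ by 80.6 − 71.4 = 9.2 percentage points if ungraded patients were dropped.

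**3. Effect of the order.** Assumed Grades 1/2/3/4 = 10/8/8/9 in 35 patients. Suppose k Grade 2 patients are spared dialysis but end with CRR below 70%, and so move to Grade 3.

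| k | Grades 1/2/3/4 | Dialysed | Grade ≥3 | Mean grade |
|---|---|---|---|---|
| 0 | 10/8/8/9 | 17/35 = 48.6% | 17/35 = 48.6% | 86/35 = 2.46 |
| 4 | 10/4/12/9 | 13/35 = 37.1% | 21/35 = 60.0% | 90/35 = 2.57 |
| 8 | 10/0/16/9 | 9/35 = 25.7% | 25/35 = 71.4% | 94/35 = 2.69 |

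Dialysis falls while Grade ≥3 and the mean grade rise. Grade ≥2 stays at 25/35 = 71.4% and Grade 4 at 9/35 = 25.7% throughout. The reversal therefore needs this particular move and an ordinal, mean-grade or Grade ≥3 analysis. Sparing dialysis otherwise moves a patient from Grade 4 to 3, or from Grade 2 to 1 when urine was immediate; both are improvements.

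**The case against.** The strongest reply concerns the order. A reader might infer that Grade 3 above Grade 2 is an error because the protocol equates DGF with dialysis. The documents do not support that. The Introduction calls dialysis the most used definition, but it also says that the requirement is not standardised and that the decision varies between centers, and it lists seven alternatives, several of them based on creatinine. The primary endpoints in Section 4.6.1.1 likewise include creatinine criteria for patients who are not dialysed. Putting day 7 CRR ahead of a discretionary dialysis decision is consistent with that. This part of the objection stands.

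It is also fair that exact ties at 70% are negligible. Equality marks differ elsewhere between the synopsis and the body (the top cold ischemia band and the INR limit), so a lost mark cannot be excluded. Counting 5 empty combinations of 12 would overstate the gap, since 4 are ties and combinations are not equally likely.

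Finally, any dialysis, session counts, daily creatinine and urine output are endpoints in their own right, so a flawed composite hides little, and a lowest grade that means good function is normal for a severity scale. Both points limit the damage. Neither gives the slow-urine patient a grade or says where DGF begins.

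**Conclusion.** The scale is not exhaustive. One of 8 combinations of urine onset, dialysis and CRR has no grade, and nothing else in the protocol repairs it. This follows from the text without assumptions. How many patients it affects cannot be derived, because the documents give no frequency and do not define immediate urine production. A reader might infer that a given number per arm will be lost from the endpoint, but the plan does not say that ungraded patients are dropped; the percentages above rest on assumed counts and show direction only.

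That the plan does not say which grades count as DGF is also plain from the text.

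The order of Grades 2 and 3 is a caution and not an error. A reader might apply the 50% and 25% DGF rates of Section 6.2 and infer that about 9 of 35 patients (0.25 × 35 = 8.75) would be scored as worse. Those rates are not tied to this scale, and only spared Grade 2 patients who finish with CRR below 70% would move that way. Their share is unknown, and the plan specifies none of the analyses in which it would matter.

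The consequence is confined to one secondary endpoint, with some bearing on the choice of a Phase III endpoint.

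**What to change.** In Sections 2.2 and 4.6.1.2:

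- define Grade 1 as no dialysis with CRR of at least 70%, and report urine output separately;
- use at least 70% in Grade 2 as well;
- state that Grade 1 is not counted as DGF;
- report the dialysis and day 7 CRR components beside the grade, so that a move between Grades 2 and 3 can be read for what it is.

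With these changes all 12 combinations have a grade. Merging Grades 2 and 3 is possible but not required: it removes the disputed order at the price of treating dialysed and never-dialysed patients alike.

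The cost is wording and a small departure from the scale as it stands in the protocol. Counting Grades 2 to 4 as DGF includes never-dialysed patients with CRR below 70%, which is broader than the dialysis definition and is a further reason to show the components. No new data are needed: creatinine, dialysis and urine output are already scheduled, and Appendix A requires day 7 laboratory tests even after earlier discharge.
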